### 5.6. Compliance measure

No specific compliance measures are designed for the use of ECS and LMWH injections. The compliance with the IPC device will be measured as follows. Every day, the investigator (weekdays) or surgeon on duty (weekends and holidays) should visit a patient five times and check that, if the subject is confined to bed, the sleeves are applied to his legs and that the pump is functioning. The results of such visits should be registered in a specifically designed compliance sheet (Fig. 4). The compliance will be calculated as a proportion of all marks testified that IPC was applied to the total number of visits that found patient in the bed.

		Visit 1	Visit 2	Visit 3	Visit 4	Visit 5	Compliance
Day X	Patient is in bed	√	√	√	√	√	100%
	IPC is turned on	√	√	√	√	√	
Day Y	Patient is in bed	√	-	-	-	√	100%
	IPC is turned on	√	-	-	-	√	
Day Z	Patient is in bed	√	√	√	√	√	40%
	IPC is turned on	√				√	

**Figure 4.** An example compliance sheet, which assessed compliance with IPC. The right column represents the result of the calculations.

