#### **4.3. Sequential pneumatic compression**

Intermitted pneumatic compression should be applied with Cardinal Health™ Kendall SCD™ 700 Series Controller and Kendall SCD™ thigh-length Comfort Sleeves. The pumps will be provided by the Sponsor (10 pumps by Cardinal Health™), and the sleeves will be purchased by the Clinical centers. Sleeves should be fitted according to the manufacturer's instructions and used in a disposable manner. Sleeves should be changed when they become soiled or lost their fixation.

IPC should be started just before the surgery in the operating room during general anesthesia induction or after regional anesthesia application before covering the operating field with the sterile material. Also, it is allowed to apply IPC within 12 h after surgery. The main conditions of IPC application are as follows: no venous thrombosis

confirmed by DUS, no skin lesions on the leg, no signs of skin and soft tissue infections of the legs, ABI >0.6.

IPC should be applied around-the-clock in the ICU, and at the time of bed-rest with a 6 h free-of-compression interval from 0 am to 6 am in the profile surgical department. The IPC required to be used during the whole inpatient treatment period.

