#### **5.4. Examination during inpatient treatment**

The following data on surgical procedure should be obtained from the medical records after intervention: the surgical profile (e.g., abdominal, thoracic, neck, pelvis, cranial), type of surgery (open, endoscopic, endoscopy assisted), urgency of surgery (emergent = performed in 0–2 h after admission, urgent = performed in 0–6 days after admission, elective = performed independently at the time of admission), radicalism of surgery (radical, palliative), type of anesthesia (general, regional, combined), surgery duration, blood loss, and intraoperative infusion.

The routine clinical examination of the patient will be performed in a daily manner with special attention to the possible complications, such as DVT, SVT, PE, bleeding, and leg skin injury. IPC sleeves should be removed for 15–20 mins every day for skin inspection and investigation of pedal pulsation. Consultation of any relevant specialist

(cardiologist, neurologist, pulmonologist, infections) should be performed if any complication or development of new co-morbidity will be observed during the follow-up.

DUS should be performed every 3–5 days after surgery and in emergency manner if any clinical suspicion for DVT or SVT appeared. In an emergency manner, DUS may be performed by a blinded expert or specialist on duty on weekend and holidays. However, all conclusions of non-investigational medical staff must be verified by a blinded expert.

SPECT/CT or CTPA should be used to verify PE in an emergency manner if clinical suspicion appeared. An autopsy must be performed in all died patients to verify the absence of DVT and PE.

In case of any clinical suspicion for a VTE event, IPC should be interrupted until final verification of the diagnosis. In the case of positive DUS, CTPA, and SPECT/CT, the therapeutic anticoagulation should be prescribed, and IPC should be removed. In the case of clinical suspicion for VTE with negative results of instrumental tests, IPC should not be returned until the proper diagnosis that mimics VTE will be found.

Any revealed leg skin lesion should be judged individually for the possibility to continue ECS and IPC application. If the decision will be made to stop IPC, the patient should be withdrawn from the study according to the protocol.

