## 8. Statistical analysis plan and sample size calculation

**Statistical analysis plan.** The primary statistical analysis is designed as intention-to-treat with the use of two-tailed Fisher's exact test to compare the primary endpoint between two groups. The primary endpoint will be reported as an absolute number, percentage, and relative risk with 95% CI. Secondary statistical analysis of the primary endpoint will be made using an unadjusted Cox proportional-hazards model. The data will be censored on the time of VTE registration, or death, or discharge from the hospital and reported as a hazard ration with 95% CI. Kaplan-Meier curves will be used to compare time-to-event distribution. Cox proportional-hazards models adjusted for the clinical center, surgery profile, type of surgery, emergency of surgery, type of anesthesia, surgical radicalism, malignant disorder, Caprini score, and time to start LMWH injections will be used.

A similar analysis for the per-protocol population, but that excluded patients with gross violations of the protocol and premature discontinuation of at least one component of combined prophylaxis (ECS, IPC or LMWH), will be performed for the primary endpoint.

Secondary endpoints will be analyzed with two-tailed Fisher's exact test and will be represented as an absolute number, percentage, and relative risk with 95% CI.

Cox proportional-hazards models will be used for the prespecified subgroup analysis for the following subgroups: surgical profile; type of surgery; the urgency of surgery; the radicalism of surgery; type of anesthesia; malignant or benign disorder; preoperative, postoperative, or delayed start of LMWH injections; and pre-operative or post-operative IPC application.

Sensitivity analysis will address to the per-protocol analysis, compliance with IPC (restricted for 90% and more), duration of follow-up (restricted to 7 days and more), and the number of postoperative DUS (restricted with two and more).

Missing data on the primary endpoint are not anticipated in the inpatient settings, so no analysis for missing data being planned.

Adjusting for multiple comparisons and imputation for missing values will not be performed. The 95% confidence intervals will be not adjusted for multiplicity, and therefore, inferences drawn from these intervals might be not reproducible. The interim analysis is not planned.

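### The IPC compliance formula counts in-bed visits as failures even when the protocol orders or allows IPC to be off, so a patient who follows the regimen fully can fall below the 90% cut-off

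*Combined protocol and SAP*

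**What the plan says.** All references are to the combined protocol and SAP.

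- **Section 5.6 (Compliance measure).** Each day the investigator or the duty surgeon "should visit a patient five times and check that, if the subject is confined to bed, the sleeves are applied to his legs". Pump function is checked at the same time. Compliance is "calculated as a proportion of all marks testified that IPC was applied to the total number of visits that found patient in the bed". The sheet in Figure 4 has two rows per day, one for being in bed and one for the device running. Its example days score 100%, 100% and 40%. Visits out of bed drop out (Day Y). In-bed visits without IPC count as failures (Day Z). There is no field for the reason.
- **Section 5.4 (inpatient examination).** The rule on suspicion reads: "In case of any clinical suspicion for a VTE event, IPC should be interrupted until final verification of the diagnosis". After negative tests, "IPC should not be returned until the proper diagnosis that mimics VTE will be found". After a positive test, "the therapeutic anticoagulation should be prescribed, and IPC should be removed". The sleeves also come off for 15 to 20 minutes a day for a skin check.
- **Section 4.3 (pneumatic compression).** On the start of treatment: "Also, it is allowed to apply IPC within 12 h after surgery". In the surgical department, though not in the ICU, there is no compression from midnight to 6 am.
- **Section 3.1.** The device is taken off before a bedside ultrasound by the blinded expert.
- **Section 8.** The sensitivity analyses include "compliance with IPC (restricted for 90% and more".

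Compliance with IPC is a secondary endpoint (section 3.5). Compliance under the regimen with the night interval is a secondary objective (section 2). No section removes ordered or allowed off-time from the denominator, or says that the sheet is paused meanwhile.

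**The concern.** The objective asks whether patients keep to a defined regimen, and that regimen includes periods when IPC must be off or may be off. The formula does not recognise those periods. A check that finds the patient in bed with the device off is a failure, whether the patient refused it or the protocol ordered it off. With two marks per visit, the two cases cannot be separated later from the sheet.

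Two results depend on this number. The compliance endpoint would understate adherence by an unknown amount. The 90% restriction could also remove fully adherent IPC patients because a VTE was suspected and worked up. Control patients have no IPC compliance, so the filter acts on one arm only.

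**Working it through.** **Inputs.** Five visits a day (section 5.6). Cut-off 90% (section 8). Length of stay and length of interruption are not given. I take stays of 5 to 21 days, with 7 days as the reference because section 4.2 requires at least 7 days of LMWH. The patient is assumed to wear IPC at every in-bed visit at which it is required.

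**Step 1: reproduce Figure 4.** Compliance = IPC-on marks / in-bed visits. Day X: 5/5 = 100%. Day Y: 2/2 = 100%. Day Z: 2/5 = 40%. All three match, so the formula is read as the plan intends. Section 5.6 does not say whether days are pooled or averaged over a stay. With the same number of in-bed visits each day, the two agree.

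**Step 2: how much off-time crosses the cut-off.** With N in-bed visits, m of them during ordered or allowed off-time, compliance is (N − m)/N. This is below 90% when m > 0.10 × N. With all five visits in bed, N = 5 × stay:

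| Stay (days) | N | Largest m still at 90% or more | First m below 90% | In days off | Compliance at that m |
|---|---|---|---|---|---|
| 5 | 25 | 2 | 3 | 0.6 | 22/25 = 88.0% |
| 7 | 35 | 3 | 4 | 0.8 | 31/35 = 88.6% |
| 10 | 50 | 5 | 6 | 1.2 | 44/50 = 88.0% |
| 14 | 70 | 7 | 8 | 1.6 | 62/70 = 88.6% |
| 21 | 105 | 10 | 11 | 2.2 | 94/105 = 89.5% |

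With three in-bed visits a day, the first failing counts are 3 of 21 (7 days) and 5 of 42 (14 days).

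**Step 3: whole days off.** For d days off in a stay of L days, compliance is 1 − d/L, which is below 90% when L < 10 × d. One full day fails any stay under 10 days; two days fail any stay under 20. One day off gives 20/25 = 80.0% at 5 days, 30/35 = 85.7% at 7, 45/50 = 90.0% at 10 (kept), 65/70 = 92.9% at 14 and 100/105 = 95.2% at 21.

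**Step 4: a short work-up.** One or two visits lost in a 7-day stay leave 34/35 = 97.1% or 33/35 = 94.3%. The patient stays in the set.

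**Step 5: the other sources.**
- Night interval: if one of the five visits fell between midnight and 6 am every day, with the patient in bed in the surgical department, the maximum would be 4/5 = 80%. Visit times are not stated, so this is a possibility only.
- Start up to 12 h after surgery: if visits were spread evenly over 24 h, 5 × 12/24 = 2.5, so two or three visits. At 7 days that leaves 33/35 = 94.3% or 32/35 = 91.4%. Alone it does not cross the cut-off on that assumption, but it adds to other losses.
- Skin check: 20 min is 20/1080 = 1.9% of 18 h or 20/1440 = 1.4% of 24 h. Alone it would rarely matter.
- Bedside ultrasound: the time off is not given.

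**Step 6: after the change.** If off-time under the protocol leaves the denominator, the 7-day patient with one ordered day off scores 30/30 = 100% instead of 30/35 = 85.7%.

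**The case against.** The best defence is that section 5.6 describes exposure: the share of in-bed checks with IPC running. Restricting a sensitivity analysis to high exposure is legitimate. What stands is that exposure is worth reporting. It is not, however, the adherence to a regimen with planned off-time that the section 2 objective names.

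The second defence is that work-ups are short. Section 5.4 calls for emergency imaging, and step 4 shows that a one- or two-visit interruption does no harm at 7 days. That limits the claim. It does not cover suspicion with negative tests, where the interruption has no upper limit.

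A reader might go further than the documents allow in three ways.

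- *Every patient with a suspected VTE leaves the 90% set.* This is not supported, because the result depends on the ratio of interruption to stay, and neither is given.
- *A confirmed VTE wrecks the score because the sheet runs on to discharge.* Section 3.3 makes any VTE endpoint event a withdrawal criterion, so continued counting is the less natural reading. The plan should still say when the count stops.
- *The formula creates an association between low compliance and VTE.* This is not shown. The primary endpoint is asymptomatic thrombosis, and an event found at a scheduled scan has no preceding suspicion and so no suspicion-driven interruption before it. Patients with suspicion and negative tests had no VTE confirmed at that point, so scoring them low attaches low compliance to non-events.

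**Conclusion.** The point holds in a conditional form. As written, section 5.6 scores off-time that the protocol orders or allows as non-compliance, and nothing elsewhere corrects it. A patient who follows the regimen fully *can* fall below 90%: about 0.8 day of in-bed off-time is enough in a 7-day stay and 1.6 days in a 14-day stay, if all five daily visits find the patient in bed. The clearest exposure is suspected VTE with negative tests. The number of patients affected cannot be derived from the documents.

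The consequence is limited to one secondary endpoint and one sensitivity analysis, with the filter acting on the IPC arm alone. The primary intention-to-treat Fisher test does not use compliance and is unaffected. The change is worth making because the reason for off-time may not be recoverable from a two-mark sheet.

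**What to change.** - Add a third row to the compliance sheet, *IPC off per protocol*, for visits before the permitted first application, during an ordered interruption, in the night interval, and during a skin check or bedside ultrasound.
- In section 5.6, define compliance as IPC-on marks divided by in-bed visits at which the protocol required IPC. Use this figure for the secondary endpoint and for the 90% restriction.
- State that the count ends at the first confirmed VTE or at withdrawal.
- State the visit times, or at least whether any fall in the night interval.
- Report ordered off-time separately, so that exposure can still be seen.

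The cost is one more row and a few lines of text, with no extra visits and no change to any clinical rule. The drawback is that the new figure describes adherence to the regimen rather than total exposure, which is why off-time must be reported beside it.

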different IPC manufactures (with various pumps and sleeves) according to the clinical efficacy, compliance, patient's and nurse's satisfaction. The authors found some significant differences in the incidence of DVT, which ranged from 2.0% to 9.8% among the devices ( $p = 0.003$ ), and the best figures were observed for graduated sequential compression devices (SCD): 2.5% and 2.0% respectively. However, taking into account compliance and patient's and nurse's satisfaction, the best scores were demonstrated for the tight-length intermitted compression, which was associated with a DVT rate of 3.2%.

So, the second critical concern is compliance with IPC. Usually, compliance is far from 100% and typically ranges between 48 and 53%. It seems that compliance is higher in the intensive care unit (ICU) than in the profile surgical department. The main disadvantages of the IPC devices are related to their cumbersome size and their requirement to be connected to a static power source, both of which tended to confine patients to bed and delayed hospital discharge and rehabilitation. The studies that have aimed to assess compliance with IPC report that there might be a lack of device application as well as device functions. One study found that of all IPC devices that were applied, in 16% the pump did not function during the investigator's control visits.

The third point is that the minimal time of IPC application is unclear. Various studies have reported different durations of IPC application per day (14–20 h) depending on the type of device (portable or stationary). Another trial found that IPC in addition to pharmacoprophylaxis after orthopedic procedures was effective when applied for 6 h or more. However, the usual recommendation is to achieve 18 h of daily compliance.

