These and other unresolved issues formed the basis of this study. The main hypothesis of the study was that the combination of IPC with standard preventive measures (above knee anti-embolic elastic compression stockings [ECS] and standard doses of low-molecular-weight heparin [LMWH]) would reduce the incidence of postoperative VTE in patients at extremely high risk (Caprini score of 11 or more). Also, to improve the compliance with IPC, we decided to find out if providing a 6-h free-of-compression night interval (from midnight to 6 am) with the preservation of 18 h of target duration for device application will result in better compliance combined with good clinical outcomes.

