### **Secondary objectives:**

- To study the effect of IPC on the asymptomatic venous thrombosis occurrence during inpatient treatment in prespecified groups of patients:
  - Surgical profile,
  - Type of surgery,
  - The urgency of surgery,
  - The radicalism of surgery,
  - Type of anesthesia,
  - Malignant or benign disorder;
  - Preoperative, postoperative or delayed start of LMWH injections,
  - Pre-operative or post-operative IPC application,
- To study the effect of IPC on the isolated calf muscle DVT occurrence during inpatient treatment;
- To study the effect of IPC on the proximal DVT occurrence during inpatient treatment;
- To study the effect of IPC on the symptomatic PE occurrence during inpatient treatment;
- To study the effect of IPC on the fatal PE occurrence during inpatient treatment,

- To study the effect of IPC on the total VTE events that occur during inpatient treatment,
- To study the effect of IPC on the leg skin injury occurrence during inpatient treatment;
- To study the effect of IPC on the major and clinically relevant non-major bleeding occurrence during inpatient treatment;
- To study the compliance with IPC applied in the suggested regimen-required night free-of-compression interval;
- To study the effect of IPC on the symptomatic and asymptomatic venous thrombosis of lower limbs, symptomatic pulmonary embolism occurrence, and VTE related and VTE-non-related mortality during outpatient treatment and rehabilitation 30 and 180 days after surgery.

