#### **Secondary endpoints:**

During inpatient treatment: isolated calf muscle DVT; proximal DVT; symptomatic PE; fatal PE; total VTE events; postoperative mortality; leg skin injury; combination of major and clinically, relevant non-major bleeding; and compliance with IPC.

At 30 days after surgery:

- Combination of symptomatic, asymptomatic venous thrombosis of the lower, limbs and symptomatic PE;
- VTE-related mortality;
- Non-VTE-related mortality.

At 180 days after surgery:

- Combination of symptomatic, asymptomatic venous thrombosis of the lower limbs, and symptomatic PE;
- VTE-related mortality;
- Non-VTE-related mortality.

Following DUS, distal DVT is defined as incompressibility of the affected calf vein, re-occlusion of the previously affected calf vein in case of personal DVT history. Proximal DVT is defined as incompressibility of the affected popliteal and thigh veins, re-occlusion of previously affected popliteal and thigh veins in case of personal DVT history, no blood flow with color flow imaging. Superficial vein thrombosis is defined as incompressibility of the affected superficial vein (GSV and its branches and SSV and its branches). Isolated calf muscle DVT is defined as occlusion of any calf veins except PTV, ATV, and PeV (sural veins, soleal veins). Proximal DVT is defined as occlusion of popliteal and all further cranial venous segments up to the iliac veins (PV, FV, CFV, external iliac vein, common iliac vein). Pulmonary embolism will be suspected according to the classical clinical symptoms and verified with SPECT/CT or CTPA by specific defects of contrast.

Major bleeding is defined by the ISTH criteria as: fatal bleeding; bleeding that is symptomatic and occurs in a critical area or organ; extra-surgical site bleeding causing a fall in hemoglobin level of  $\geq 20$  g/L, or leading to transfusion of  $\geq 2$  units of whole blood or RDC, with temporal association within 24–48 h to the bleeding; surgical site bleeding that requires a second intervention; or surgical site bleeding that is unexpected and prolonged or sufficiently large to cause hemodynamic instability, as assessed by the surgeon.

Clinically relevant non-major (CRNM) is defined as any other bleeding, that does not match the criteria of major but needs some specific measures for hemostasis and/or interruption or preliminary abortion of anticoagulation.

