### **5.2. VTE risk assessment**

The primary VTE risk assessment should be performed by Russian National Guidelines, and if the patient will be classified as having a high risk (major surgery in subjects over 60 years old or major surgery in subjects from 40 to 60 years old having additional individual risk factors for VTE), he should be assessed by Caprini score. A Russian adaptation of the 2005 version of the Caprini score will be used (Fig. 3).

The primary risk assessment will be performed before randomization. Any patients that will receive or will be supposed to receive (e.g., supposed prolonged bed rest in ICU, supposed malignancy, CHF, COPD, bowel inflammatory disease, thrombophilia, etc.) a score of 11 or more, should be invited into the study. The calculation of the final Caprini score should be done before discharge or after patients' death. So, all new condition and complications occurred during the inpatient treatment period will be considered. However, some enrolled patients may decrease their score because of unexpected early ambulation, misdiagnosis of malignant disease or other co-morbidities.

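### The IPC compliance proportion combines ICU checks (no night break) with ward checks (0–6 am break), so it does not describe compliance under the night-break regimen that the secondary objective names

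*Combined protocol and SAP*

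**What the plan says.** Section 1 (Background) gives the reason for the night break: "to improve the compliance with IPC, we decided to find out if providing a 6-h free-of-compression night interval", keeping an 18-hour daily target, would lead to better compliance with good clinical outcomes. Section 2 turns this into a secondary objective: "To study the compliance with IPC applied in the suggested regimen-required night free-of-compression interval". Section 3.5 lists the endpoint simply as "and compliance with IPC".

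Section 4.3 sets different schedules by setting. IPC is to run "around-the-clock in the ICU, and at the time of bed-rest with a 6 h free-of-compression interval from 0 am to 6 am", and the sentence ties the break to the surgical department. IPC is required for the whole inpatient stay, so checks can come from both settings.

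Section 5.6 asks for five checks a day and defines compliance as the "proportion of all marks testified that IPC was applied to the total number of visits that found patient in the bed". The example sheet in Figure 4 has one row for being in bed and one for the pump being on, with a percentage for each day. It has no field for setting, and no clock times are given for the checks.

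Section 8 adds no split of compliance by setting, and ICU stay is not among its subgroups. Its rule for secondary endpoints is a two-group Fisher's exact test, with results that "will be represented as an absolute number, percentage, and relative risk with 95% CI". Such a comparison cannot apply to a measure taken in the IPC arm only.

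**The concern.** The objective names a regimen with a night break, but the formula also counts checks from a setting where no break is given. Two further statements suggest that this matters in practice. Section 5.2 gives "supposed prolonged bed rest in ICU" as an example of what may count towards an eligible Caprini score, so some ICU time is foreseen. The Background says "It seems that compliance is higher in the intensive care unit (ICU) than in the profile surgical department".

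At stake is the reading of one descriptive secondary endpoint. A favourable pooled figure could owe much to ICU days, on which the break was not used, and still be taken as support for the break.

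**Working it through.** **1. Reproduce the plan's own example.** Compliance = IPC-on marks / in-bed marks (section 5.6, Figure 4).

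- Day X: 5/5 = 100%
- Day Y: 2/2 = 100%
- Day Z: 2/5 = 40%

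All three match Figure 4. The text does not say how days are combined over a stay. Summing marks gives (5+2+2)/(5+2+5) = 9/12 = 75%; averaging the daily values gives (100+100+40)/3 = 80%. The wording of the formula points to summing, but the sheet shows daily results.

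**2. Set the objective against the formula.**

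| Item | ICU | Surgical ward |
|---|---|---|
| Schedule (section 4.3) | continuous | during bed rest, off 0–6 am |
| Regimen named in the objective (section 2) | no | yes |
| Counted in the formula (section 5.6) | yes | yes |

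The in-bed denominator itself is right, because ward IPC is ordered only at bed rest. The mismatch lies in combining the two columns.

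**3. Effect of pooling when marks are summed.** Let f be the ICU share of in-bed marks, I the ICU compliance and W the ward compliance.

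Pooled = f × I + (1 − f) × W, so pooled − W = f × (I − W).

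The documents give neither f, I nor W. The values below are assumptions chosen to show a range, in percentage points:

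| f | I − W = 10 | I − W = 20 | I − W = 30 |
|---|---|---|---|
| 20% | 2.0 | 4.0 | 6.0 |
| 1/3 | 3.3 | 6.7 | 10.0 |
| 50% | 5.0 | 10.0 | 15.0 |

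If I = W, or if there are no ICU marks, the difference is zero. If I is below W, the sign reverses.

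**4. Dependence on how days are combined.** Assume 2 bed-bound ICU days (2 × 5 = 10 marks, all on) and 5 ward days with two in-bed checks each, as on Day Y (5 × 2 = 10 marks, 8 on).

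- Ward: 8/10 = 80%.
- Marks summed: (10+8)/20 = 90%, which is 10 points above the ward figure. Here f = 10/20 = 50%, although ICU days are only 2/7 = 28.6% of the stay, because a bed-bound patient supplies more marks per day.
- Daily values averaged: (2 × 100 + 5 × 80)/7 = 600/7 = 85.7%, which is 5.7 points above.

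**5. A possible offset.** The formula does not exclude ward checks between 0 and 6 am. If one of five in-bed ward checks fell in the break, a fully adherent patient would score 4/5 = 80%. With ICU at 100% and f = 50%, the pooled figure would be 0.5 × 100 + 0.5 × 80 = 90%, now 10 points below the true ward compliance of 100%. The documents do not say whether such checks occur.

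**The case against.** The strongest reply is that section 4.3 describes a single package (continuous in the ICU, then bed-rest use with a break on the ward) and that section 3.5 lists only compliance with IPC. On that reading, whole-stay compliance is the intended measure. This is possible, but it fits poorly with an objective that names the night interval and a Background that sets an 18-hour target, which cannot describe round-the-clock ICU use. Even if the package is meant, the pooled figure cannot be credited to the break.

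Several other points stand and limit the finding:

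- The direction rests on one hedged Background sentence that gives no size, and break-time ward checks would push the other way.
- Section 5.2 shows that ICU stays are foreseen, not how common they are.
- Figure 4 also gives daily values, and averaging these would reduce the ICU weight in the example above.
- The setting may be recoverable later from transfer dates. What is then missing is prespecification, and transfer days would be ambiguous.

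A reader might go further and infer that the trial's compliance will be inflated by a known amount, or by as much as 15 points. The documents do not support that, because every input to that range is assumed. A reader might also infer that the sensitivity analysis restricted to compliance of 90% or more is invalid. That restriction asks whether IPC was delivered as prescribed, and for this purpose a whole-stay figure is reasonable. Finally, a reader might infer that a ward-only figure would answer whether the break gives better compliance. It would not: no group receives ward IPC without the break.

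**Conclusion.** The point holds in a limited form. Followed as written, the plan produces a compliance figure that mixes two regimens, and nowhere defines the ward figure to which the night-break objective refers. This follows from the text of sections 2, 4.3, 5.6 and 8 and needs no numerical assumption.

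The size does not follow from the text. If ICU compliance exceeds ward compliance, summed marks overstate the ward figure by f × (I − W), which is 2 to 15 points over the assumed grid. The net bias could be smaller or reversed, depending on how days are combined and when ward checks are made. Only a descriptive secondary endpoint is affected; the primary endpoint and its analysis are not.

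**What to change.** - Add an ICU/ward tick for each check on the compliance sheet. Linking to ICU transfer dates is an alternative, less exact on transfer days.
- Exclude ward checks made between 0 and 6 am from the denominator, since IPC is correctly off then. This needs the time of each check, or a rule that ward checks are made outside those hours.
- State in section 5.6 whether marks are summed over the stay or daily values averaged.
- In section 8, prespecify the ward-only in-bed proportion as the descriptive result for the night-break objective, with the ICU and pooled figures beside it.
- State that, without a no-break comparator, the ward figure describes compliance under the break and does not show that the break improves it.

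The five daily checks, the in-bed principle and the 90% threshold can stay. If any break-time ward checks are made, excluding them would also correct the pooled figure to which that threshold is applied. The cost is slightly more recording and a few sentences in sections 5.6 and 8, with no extra visits. The downside is that fewer marks stand behind the ward figure, which may also look less favourable than the pooled one.
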